1. VERSION HISTORY

Table 1. Summary of Changes

Version/ Date	Associated Protocol Amendment	Rationale	Specific Changes
1.0 10 Dec 2020	Original 5 th Oct 2020	N/A	N/A

2. INTRODUCTION

This statistical analysis plan (SAP) provides the detailed methodology for summary and statistical analyses of the data collected in Study C3421014. This document may modify the plans outlined in the protocol; however, any major modifications of the primary endpoint definition or its analysis will also be reflected in a protocol amendment.

2.1. Study Objectives, Endpoints, and Estimands

Objectives	Endpoints
Primary	Primary
To compare the PK of PF-06882961 following administration of a single oral dose in adult participants with varying degrees of hepatic impairment relative to age- and body weight-matched participants without hepatic impairment.	Plasma: C_{max}, AUC_{inf}, AUC_{last}, fu as data permit.
Secondary	Secondary
To evaluate the safety and tolerability of a single oral dose of PF-06882961 when administered to adult participants with varying degrees of hepatic impairment and in age- and body weight-matched participants without hepatic impairment.	Assessment of treatment emergent AEs, clinical laboratory abnormalities, vital signs, ECG parameters.
Tertiary/Exploratory	Tertiary/Exploratory
To compare additional PK parameters of PF-06882961 following administration of a single oral dose in adult participants with varying degrees of hepatic impairment and in age- and body weight-matched participants without hepatic impairment.	Plasma: $C_{max,u}$, $AUC_{inf,u}$, $AUC_{last,u}$, CL/F, $CL_{u/F}$, $V_{z,F}$, $V_{z,u/F}$, T_{max}, $t_{1/2}$ as data permit.

There are no estimands for this study.

2.2. Study Design

This is a non-randomized, open-label, single-dose, parallel-cohort, multicenter study to investigate the effect of varying degrees of hepatic function on the plasma PK of

PF-06882961 after a single, oral 20 mg dose administered in the fed state. A total of approximately 24 participants with varying degrees of hepatic function will be dosed in the study as shown in Table 2.

Table 2. Hepatic Function Categories Based on Child-Pugh Score

Cohort	Description	Child-Pugh Score	Number of Participants
1	Without hepatic impairment	Not Applicable	6 ^a
2	Mild hepatic impairment	Class A (5 to 6 points)	6
3	Moderate hepatic impairment	Class B (7 to 9 points)	6
4	Severe hepatic impairment	Class C (10 to 15 points)	6 ^b

[figure not shown]
- a. Additional participants may be dosed to a maximum of 8 participants to ensure mean age ± 5 years and mean body weight ± 10 kg of this cohort is aligned with the pooled average assessed when $\geq 75\%$ of participants are dosed across the other 3 cohorts.
- b. If recruitment across the sites selected proves to be prohibitive, study will dose only 4 participants in this cohort.

Categorization of participants into Cohort 2-4, inclusive, will be done based on Child-Pugh scores determined, as described in Appendix 8 (of the protocol) at the screening visit.

Participants will be dosed in a staged manner such that those with moderate and severe hepatic impairment (Cohorts 3 and 4) will be evaluated first. Recruitment for participants with mild hepatic impairment (Cohort 2) will initiate when approximately 50% of the total participants in Cohorts 3 and 4 have been dosed. Participants without hepatic impairment (Cohort 1) will be recruited near the end of the study to match the average demographics (at a minimum, age and weight; and gender as much as practically possible) across the pooled Cohorts 2 through 4.

Participants who prematurely discontinue before completing all assessments may be replaced, at the discretion of the principal investigator (PI) and sponsor study team.

The overall study design is summarized in Figure 1.

Figure 1. Study Schema

3. ENDPOINTS AND BASELINE VARIABLES: DEFINITIONS AND CONVENTIONS

Blood samples for PK analysis of PF-06882961 will be collected according to the Schedule of Activities given in the protocol.

PK parameters will be calculated (if possible) from the concentration-time data using standard non-compartmental methods.

3.1. Primary Endpoint(s)

- PF-06882961 Plasma Pharmacokinetic parameters: C_{max} , AUC_{inf} , AUC_{last} , fu as data permit.

The plasma PK parameters in Table 3 will be determined using standard non-compartmental methods:

Table 3. Summary of Plasma PK Parameters of PF-06882961 to be calculated

Parameter	Analysis Scale	PF-06882961 20mg
C_{max}	ln	A, D
AUC_{inf}^*	ln	A, D
AUC_{last}	ln	A, D
fu	ln	A, D

*=if data permits. Abbreviations: A = analyzed using a statistical model; D=displayed with descriptive statistics as outlined in [Table 6](#) in Section [6.1.1.1](#); ln=natural-log transformed; R=raw (untransformed).

3.2. Secondary Endpoint(s)

- *Assessment of treatment emergent AEs, clinical laboratory abnormalities, vital signs, ECG parameters.*

An adverse event is considered treatment emergent (TEAE) relative to a given treatment if:

- the event starts during the effective duration of treatment (i.e. starting on or after the dose of PF-06882961 but before this dose plus lag time)

The effective duration of treatment is determined by the lag time. Any event occurring within the lag time is attributed to the corresponding treatment. The lag time is defined by the Pfizer Standard of 365 days post last dose of IP.

A 3-tier approach for summarizing AEs will not be used due to the low number of participants planned to be recruited.

The following data are considered in standard safety summaries (see protocol for collection days and list of parameters):

- adverse events,
- laboratory data,
- vital signs data,
- ECG results.

For laboratory, vital signs and ECG data, baseline will be defined as the last pre-dose measurement on Day 1 or before.

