### **8.3.1.2. Recording Nonserious AEs and SAEs on the CRF**

All nonserious AEs and SAEs occurring in a participant during the active collection period, which begins after obtaining informed consent as described in [Section 8.3.1](#), will be recorded on the AE section of the CRF.

The investigator is to record on the CRF all directly observed and all spontaneously reported AEs and SAEs reported by the participant.

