### **10.3. Appendix 3: Adverse Events: Definitions and Procedures for Recording, Evaluating, Follow-up, and Reporting**

#### **10.3.1. Definition of AE**

AE Definition

• An AE is any untoward medical occurrence in a patient or clinical study participant, temporally associated with the use of study intervention, whether or not considered related to the study intervention.

• NOTE: An AE can therefore be any unfavorable and unintended sign (including an abnormal laboratory finding), symptom, or disease (new or exacerbated) temporally associated with the use of study intervention.

Events Meeting the AE Definition

• Any abnormal laboratory test results (hematology, clinical chemistry, or urinalysis) or other safety assessments (eg, ECG, radiological scans, vital sign measurements), including those that worsen from baseline, considered clinically significant in the medical and scientific judgment of the investigator. Any abnormal laboratory test results that meet any of the conditions below must be recorded as an AE:

• Is associated with accompanying symptoms;

• Requires additional diagnostic testing or medical/surgical intervention;

• Leads to a change in study dosing (outside of any protocol-specified dose adjustments) or discontinuation from the study, significant additional concomitant drug treatment, or other therapy.

• Exacerbation of a chronic or intermittent preexisting condition including either an increase in frequency and/or intensity of the condition.

• New conditions detected or diagnosed after study intervention administration even though it may have been present before the start of the study.

• Signs, symptoms, or the clinical sequelae of a suspected drug-drug interaction.

• Signs, symptoms, or the clinical sequelae of a suspected overdose of either study intervention or a concomitant medication. Overdose per se will not be reported as an AE/SAE unless it is an intentional overdose taken with possible suicidal/self-harming intent. Such overdoses should be reported regardless of sequelae.

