#### **Follow-up of AEs and SAEs**

- The investigator is obligated to perform or arrange for the conduct of supplemental measurements and/or evaluations as medically indicated or as requested by the sponsor to elucidate the nature and/or causality of the AE or SAE as fully as possible. This may include additional laboratory tests or investigations, histopathological examinations, or consultation with other healthcare providers.
- If a participant dies during participation in the study or during a recognized follow-up period, the investigator will provide Pfizer Safety with a copy of any postmortem findings including histopathology.
- New or updated information will be recorded in the originally completed CRF.
- The investigator will submit any updated SAE data to the sponsor within 24 hours of receipt of the information.

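### The SAP defines a treatment-emergent adverse event by onset alone, so an event open at dosing that worsens afterwards is not classed as treatment-emergent unless the site re-records it as a new event

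*SAP*

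**What the plan says.** The secondary endpoint in SAP 3.2 is "Assessment of treatment emergent AEs, clinical laboratory abnormalities, vital signs, ECG parameters". An event is treatment-emergent if "the event starts during the effective duration of treatment (i.e. starting on or after the dose of PF-06882961", with an upper limit set by the lag time. Two sentences complete the rule: "Any event occurring within the lag time is attributed to the corresponding treatment" and "The lag time is defined by the Pfizer Standard of 365 days post last dose of IP".

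The protocol names treatment-emergent AEs as an endpoint (Sections 1.1 and 3) but does not define the term. It does set how AEs are collected and recorded:

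- Section 8.3.1.2 has AEs recorded "during the active collection period, which begins after obtaining informed consent". Section 8.3.1 runs that period to at least 28 days after dosing.
- Section 10.3.1 includes among AEs "Exacerbation of a chronic or intermittent preexisting condition including either an increase in frequency and/or intensity of the condition".
- Section 10.3.3, on follow-up of AEs and SAEs, says: "New or updated information will be recorded in the originally completed CRF".

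SAP 6.2 lists and summarises the safety endpoints of Section 3.2 under sponsor reporting standards. SAP 6.2.1 summarises adverse events by group and overall, and does not say whether the tables cover all AEs or TEAEs only.

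**The concern.** A TEAE rule is meant to separate what was already there before the drug from what appeared or got worse on it. A rule that looks only at the start date handles the first half and not the second. Someone with a mild headache opened as an AE on Day -1 that becomes severe a few hours after the dose has had an on-drug worsening, yet by start date the event belongs to the pre-dose period.

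In this study AEs are collected before dosing, so the situation can arise. Whether such a worsening counts would then depend on whether the site updates the open entry or opens another. Two sites could classify the same course of events differently. What is at stake is the correctness of the TEAE count in a descriptive safety evaluation with about 6 participants per cohort. No PK result, sample size or decision rule depends on it.

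**Working it through.** The plan states no figure on this point, so the check is mainly a reading of the passages together.

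**1. Which part of the rule does the work.** The upper limit is the dose plus 365 days. Routine AE collection ends at the follow-up contact, 28 to 32 days after dosing (Protocol 1.3, 8.3.1). In practice the upper limit excludes almost nothing, and classification turns on whether the event starts before or after the dose.

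**2. Whether the next sentence widens it.** SAP 3.2 goes on to speak of events *occurring* within the lag time, which is looser than *starting*. That sentence says which treatment an event is attributed to. It does not mention an event with earlier onset that worsens, so it cannot safely be read as a worsening clause.

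**3. How long an AE can be open before dosing.** Screening is within 28 days of dosing (Protocol Section 8). At the other end, minimum participation is about 5 weeks, or 35 days (Protocol 4.1). Subtracting follow-up leaves 35 − 32 = 3 to 35 − 28 = 7 days. The pre-dose window is thus roughly 3 to 28 days. With the longest screening it makes up 28/(28 + 32) = 47% to 28/(28 + 28) = 50% of the collection period. These shares show only that the window exists. They say nothing about how many events persist to dosing and then worsen.

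**4. Whether an open AE prevents dosing.** The Day 1 criteria (Protocol 5.2.4) cover breath alcohol, pregnancy, any Day -1 laboratory tests, sponsor approval and blood pressure. None requires an open AE to have resolved.

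**5. How each kind of event is classified.**

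- An AE that starts on or after dosing is a TEAE.
- A chronic or intermittent condition already present, not recorded as an AE, that flares after dosing becomes an AE under Protocol 10.3.1. With a post-dose onset it is a TEAE.
- An AE opened between consent and dosing that continues unchanged is not a TEAE, which is right.
- An AE opened between consent and dosing that worsens after dosing and is entered as a new event is a TEAE.
- The same AE, updated on its existing entry, is not a TEAE. This is the gap.

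**6. What one such case would do.** The smallest step in a cohort's TEAE incidence is 1/6 = 16.7 percentage points, or 1/4 = 25 points if Cohort 4 has only 4 participants. Overall incidence moves by that step only if the participant has no other TEAE. This is the granularity of the table, not an estimate of the effect.

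**The case against.** The best defence is that the protocol already captures most worsening. Section 10.3.1 makes exacerbation of a chronic or intermittent preexisting condition an AE. Section 10.3.3 directs updates to the original case report form, but does not say that a worsening must stay on the same AE line with its pre-dose start date. CRF completion instructions are not in these documents and may ask for a new entry. Serious events are reported to the sponsor whatever their TEAE label, and changes in vital signs and ECG are summarised against baseline. This stands, and it makes the gap narrow. It does not close it: nothing in the documents requires re-recording, and the exacerbation wording does not clearly reach an acute event that first opened after consent.

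A reader might infer that these events disappear from the safety summaries. The documents do not say so. SAP 3.2 lists adverse events without restriction among the data for standard safety summaries, SAP 6.2.1 does not limit its tables to TEAEs, and SAP 6.2 provides for listings. What is lost is the treatment-emergent label.

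A reader might also infer that the undercount falls on the impaired cohorts and hardly on Cohort 1. That is possible, because Cohorts 2 to 4 have chronic disease and background medication. But illness present at consent is not the same as an AE opened during screening, and its later exacerbation can be recorded as a new AE. Protocol 5.1.3 also requires stable hepatic impairment and, in general, stable medication. No AE rates by cohort are given, so a differential effect is not shown.

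**Conclusion.** The point holds as a defect in the definition. SAP 3.2 uses onset alone, and an AE that opens between consent and dosing, is ongoing at dosing and increases in severity or becomes serious afterwards is not classed as treatment-emergent unless it is re-recorded. This is a stated rule that can misclassify an on-drug worsening within the named secondary endpoint, not merely a missing detail.

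Its size cannot be estimated, because the documents give no rate of pre-dose AEs that later worsen. The conclusion assumes that at least some sites would update the open entry and keep its start date, and that the sponsor standards not reproduced here contain no worsening rule. If either assumption fails, the consequence shrinks or disappears, but the SAP text would still need to say so. The correction is worth making because it is cheap, not because a large effect is expected.

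**What to change.** Extend SAP 3.2 so that an AE is treatment-emergent if, within the lag time, it either starts on or after dosing, or was present before dosing and increases in severity or becomes serious on or after dosing.

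Add a matching CRF completion instruction: when a pre-dose AE worsens after dosing, open a new record or enter the date of the severity change. Without one or the other, the extended definition cannot be applied from the data. It would also help to state in SAP 6.2.1 whether the AE tables show all AEs, TEAEs only, or both.

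The cost is a few sentences in the SAP and one site instruction. The downside is that TEAE counts may be slightly higher.

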3.3. Other Endpoint(s)

- Additional PF-06882961 Plasma Pharmacokinetic parameters: CL/F, V_z/F, T_{max}, t_{1/2} as data permit.
- Unbound PF-06882961 Plasma Pharmacokinetic parameters: C_{max,u}, AUC_{inf,u}, AUC_{last,u}, CL_u/F, V_{z,u}/F as data permit.

The plasma PK parameters for PF-06882961 in Table 4 will be determined using standard non-compartmental methods:

Table 4. Summary of Additional Plasma PK parameters of PF-06882961 to be calculated

Parameter	Analysis Scale	PF-06882961 20mg
-----------	----------------	------------------

CL/F*	ln	D
V _z /F*	ln	D
T _{max}	R	D
t _{1/2} *	R	D

*=if data permits. Abbreviations: D=displayed with descriptive statistics as outlined in Table 7 in Section 6.3; ln=natural-log transformed, R=raw (untransformed).

The plasma PK parameters for unbound PF-06882961 will be calculated as described in Table 5:

Table 5. Summary of Plasma PK parameters of Unbound PF-06882961 to be calculated

Parameter	Method of Determination	Analysis Scale	PF-06882961 20 mg
AUC _{last,u}	fu × AUC _{last}	ln	D
AUC _{inf,u} *	fu × AUC _{inf}	ln	D
C _{max,u}	fu × C _{max}	ln	D
CL _u /F*	Dose/(AUC _{inf,u})	ln	D
V _{z,u} /F*	Dose/(AUC _{inf,u} × k _{el})	ln	D

*=if data permits. Abbreviations: D=displayed with descriptive statistics as outlined in Table 7 in Section 6.3; ln=natural-log transformed, R=raw (untransformed).

3.4. Baseline Variables

Not Applicable.

3.5. Safety Endpoints

See Section 3.2.

4. ANALYSIS SETS (POPULATIONS FOR ANALYSIS)

Data for all participants will be assessed to determine if participants meet the criteria for inclusion in each analysis population prior to releasing the database and classifications will be documented per standard operating procedures.

Participant Analysis Set	Description
Enrolled	"Enrolled" means a participant's agreement to participate in a clinical study following completion of the informed consent process.
Evaluable	All participants assigned to IP and who take at least 1 dose of IP.
Safety	All participants assigned to IP and who take at least 1 dose of IP.

Participant Analysis Set	Description
PK Concentration Set	The PK concentration population is defined as all participants who received at least 1 dose of PF-06882961 and in whom at least 1 plasma concentration value is reported.
PK Parameter Set	The PK parameter analysis population is defined as all participants who received at least 1 dose of PF-06882961 and have at least 1 of the PK parameters of interest calculated.

5. GENERAL METHODOLOGY AND CONVENTIONS

The following group labels (or similar) will be used for tables and figures unless otherwise stated:

Group	Description of Group	Label
1	Normal hepatic function	Without Hepatic Impairment
2	Mild hepatic impairment	Mild Hepatic Impairment
3	Moderate hepatic impairment	Moderate Hepatic Impairment
4	Severe hepatic impairment	Severe Hepatic Impairment

5.1. Hypotheses and Decision Rules

There is no statistical hypothesis testing planned for this study and no statistical decision rules will be applied.

5.2. General Methods

5.2.1. Analyses for Continuous Endpoints

Unless otherwise stated, continuous variables will be presented using summary statistics: number of observations, arithmetic mean, standard deviation, median, minimum and maximum values.

5.2.2. Analyses for Categorical Endpoints

Categorical variables will be presented using summary statistics: number of observations and percentages.

5.2.3. One-way Analysis of Variance (ANOVA)

The *one-way analysis of variance (ANOVA)* model will include group as a factor.

Estimates of the adjusted mean differences (Test - Reference), and corresponding 90% CIs, will be obtained from the model. These will be exponentiated to provide estimates of the ratio of adjusted geometric means (Test/Reference) and 90% CIs for the ratios. Example SAS code is given in [Appendix 1](#).

Additionally, as an exploratory analysis, age and body weight may be explored as an additional covariate in the models, as appropriate. This will be implemented by utilizing a stepwise linear regression approach, with model selection using Akaike's Information

Criterion [AIC]). All the above covariates will be considered (group as a factor will be restricted to always remain in the model) and if the final model selected includes at least one of these additional covariates, this additional model will be reported in addition to the main ANOVA model above. Example SAS code is given in [Appendix 1](#).

5.2.4. Linear Regression

Linear regression analysis will include hepatic function as a continuous explanatory variable (using continuous serum albumin, prothrombin time or total bilirubin, each modelled separately). *Estimates of the slope and intercept, together with a 90% CI, and the coefficient of determination (i.e. R-squared and adj-R-squared) will be obtained from the model.* Example SAS code is given in [Appendix 1](#).

Additionally, as an exploratory analysis, age and body weight may be explored as an additional covariate in the models, as appropriate. This will be implemented by utilizing a stepwise linear regression approach, with model selection using Akaike's Information Criterion [AIC]). All the above covariates will be considered (hepatic function will be restricted to always remain in the model) and if the final model selected includes at least one of these additional covariates, this additional model will be reported in addition to the main linear regression above. Example SAS code is given in [Appendix 1](#).

5.3. Methods to Manage Missing Data

For the analysis of safety endpoints, the sponsor data standard rules for imputation will be applied.

In all PK data presentations (except listings), concentrations below the limit of quantification (BLQ) will be set to zero. In listings BLQ values will be reported as “<LLQ”, where LLQ will be replaced with the value for the lower limit of quantification.

In PK summary tables and plots of median profiles, statistics will be calculated having set concentrations to missing if one of the following cases is true:

1. A concentration has been collected as ND (i.e. not done) or NS (i.e. no sample),
2. A deviation in sampling time is of sufficient concern or a concentration has been flagged anomalous by the pharmacokineticist.

Note that summary statistics will not be presented at a particular time point if more than 50% of the data are missing.

Participants who experience events that may affect their PK profile (e.g. lack of compliance with dosing or vomiting) may be excluded from the PK analysis. At the discretion of the pharmacokineticist a concentration value may also be excluded if the deviation in sampling time is of sufficient concern or if the concentration is anomalous for any other reason.

A full list of protocol deviations will be compiled and reviewed to identify major and minor deviations prior to database closure.

